Cardiovascular Screening for Family Members of People with Acute Coronary Disease: A Patient-Initiated and Family-Oriented Strategy

PI: [name]

Study Protocol

Patient Identification and Recruitment

The prospective study will be conducted at the Jewish General Hospital (JGH), an academic tertiary care referral centre in Montreal, Quebec. The JGH's acute care cardiovascular unit has 16 beds equipped for advanced hemodynamic and ventilator support and 32 ward beds with continuous telemetry. An outpatient cardiology clinic is adjacent to the inpatient unit.

Patients admitted to the JGH over a 12-month period will be assessed for eligibility into the study by a member of the research team. Inclusion criteria are patient age ≤ 70 years old admitted with an initial diagnosis of an acute coronary event, such as acute coronary syndrome or myocardial infarction, and at least 1 first-degree family or household member age ≥ 18 years old. Exclusion criteria are no eligible family or household members, inability to contact family or household members, distance to study centre too far as determined by the patient, or family or household members who have been screened for CV disease in the previous 2 years. Family or household members with known coronary disease will also be excluded.

Household members of the patient will be included in the study. There is evidence that partners and other non-genetically related household members, who do not have the same hereditary predisposition as the patient with CV disease, share social and lifestyle influences such as smoking habits, low physical activity, and diet, and have higher rates of CV disease than would be expected.¹

Younger relatives (≥ 18 years old) of the CV patient will be included as well. Younger relatives (typically under age 30) have been excluded from most prior screening studies.² The optimal screening and management strategy for younger relatives of CAD patients is unclear. Early risk factor assessment and counselling of younger patients may promote lifelong changes in lifestyle choices and behaviours with long-term benefits.³

Eligible patients will be given a letter containing instructions for the eligible family and/or household members on how to be referred for the initial screening visit and information about the importance of CV disease primary prevention (Appendix A). If there has been no contact from an eligible family or household member two weeks following the CV patient's hospital discharge, a member of the healthcare team will contact the CV patient by phone to remind him or her to contact eligible family or household members.

Informed consent for participation in the study will be obtained from the patient at the time of enrolment during index hospitalization and other participants at the time of the initial screening visit. Institutional research ethics approval will be obtained for this study.

Cardiovascular Screening for Family Members of People with Acute Coronary Disease: A Patient-Initiated and Family-Oriented Strategy

PI: [name]

Risk Factor Screening and Treatment

An appointment will be offered within two to four weeks of the patient's hospitalization in order to maximize the motivation of family members who are willing to undergo screening. Prior to the initial visit, participants will receive blood test requisitions for a baseline complete blood count, electrolytes, creatinine, lipid profiles, hemoglobin A1c, fasting blood glucose levels, liver enzymes, and creatine kinase. At the initial screening visit, a targeted history and physical exam will be performed by a cardiologist and investigations will be ordered as needed. CV primary prevention assessment will follow the Canadian Cardiovascular Society's recommendations.⁴ Weight and body-mass index will be recorded and blood pressure will be checked with the BPtru machine (BpTRU Medical Devices, Coquitlam, BC) in accordance to the Hypertension Canada's guidelines.⁵ A modified 10-year Framingham risk score will be calculated.⁴ In patients \leq 30 years old, a 30-year Framingham risk score will also be obtained. Physical activity will be measured using the Paffenbarger physical activity questionnaire (Appendix B) and reported in kilocalories of energy expenditure per day (kcal/d).⁶ A nutrition questionnaire (Food Frequency Questionnaire) will be administered (Appendix C). Identified CV risk factors will lead to appropriate evidence-based, society-recommended management.^{4, 5} Participants will be referred to nutritionists, smoking cessation programs, and to other allied healthcare professionals as needed. The results of the risk assessment will be shared with the participant in order to support shared decision making, which has been shown to improve the likelihood that patients will achieve target lipid levels.⁴ If the participant has a primary care physician, the physician will be sent a letter explaining the screening findings and treatment plan.

Participants will have a follow-up visit at 6-months during which they will undergo a history and physical exam and have lipid and glucose blood tests drawn. The Paffenbarger physical activity scale, Food Frequency Questionnaire, and an Information Assessment Method questionnaire (see section A3) will be administered. Interim follow-up appointments (maximum 2 per participant) may be scheduled if needed. At the 6-month visit, participants will receive an individualized report of CV risk factor control and their change in 10-year modified CV risk. Reports will be sent to the primary care physician if applicable. Participants without primary care physicians will be given resources on how to register for one.

The patient with coronary disease and all participating family and household members will be encouraged to attend the initial screening visit and all subsequent healthcare interactions. The history and physical exam will be done without other participants present in order to preserve confidentiality. Patients who accompany their family and household members to the appointments will also be encouraged to take their secondary preventive medications and continue follow-up with their treating physician, since half of patients who have a myocardial infarction stop taking their evidence-based preventative medications within 12 months of the index event.⁷

Cardiovascular Screening for Family Members of People with Acute Coronary Disease: A Patient-Initiated and Family-Oriented Strategy

PI: [name]

Assessment of Participant Comprehension and Engagement in Care

At the 6-month clinic visit, the Information Assessment Method (IAM), a self-administered 1-page questionnaire (Appendix C), will be distributed to participants (patients, family members, and household members). The IAM is will be used to systematically evaluate the (1) acquisition and relevance of new information, (2) practical impact, (3) expected health benefits, and (4) associated barriers or facilitators.^{8, 9} Using a mixed-methods approach, we will review the IAM responses to understand the factors associated with the referral and screening program and to generate recommendations and feedback to the participants. The IAM is considered a knowledge translation tool by the Canadian Institute for Health Research.¹⁰

Data Collection

A research assistant will be based in the Division of Cardiology at the JGH and will have a dedicated space in the clinical research department with a computer-equipped workstation. The research assistant will be responsible for obtaining informed consent and extracting data from the patient record.

From the patient, we will collect the following data: age, sex, ethnicity, willingness to refer family members and reasoning, whether CV screening was done prior to hospitalization, CV risk factors (including family history of CV disease), description of the acute coronary event, cardiac unit and hospital length of stay, and approximate number of eligible family or household members.

From the family or household members, we will collect the following data: age, sex, gender, ethnicity, relationship with CV patient, whether the patient has a primary care physician and last time seen, CV symptoms on history, medications, weight, BP Tru recording, physical examination findings, physical activity, nutrition, and other CV risk factors identified (i.e., obstructive sleep apnea). Baseline and 6-month CV individual risk factor values will be recorded (i.e., blood pressure, lipid levels, HbA1c), as well as baseline and 6-month modified Framingham 10-year risk scores. A 30-year Framingham risk score will be recorded at baseline and 6-months for patients who are under age 30 at the time of study enrolment. Results from the IAM, nutrition, and physical activity at the 6-month visit will also be collected.

Measures

The effectiveness of the screening strategy will be measured by the total number of participants identified at intermediate or high risk on the modified Framingham CV risk score (>10% risk of a CV event over the following 10-year period). The effectiveness of the primary prevention intervention will be measured by the change in percentage of the mean modified Framingham 10-year CV risk score for family and household members between the initial visit and 6-month follow-up. The most recent Canadian Cardiovascular Society guidelines strongly recommend CV risk assessment using the modified Framingham 10-year risk score to guide therapy and to repeat the risk assessment when there is an expected change in risk status.⁴

Cardiovascular Screening for Family Members of People with Acute Coronary Disease: A Patient-Initiated and Family-Oriented Strategy

PI: [name]

Data Analysis

Results will be stratified by age (<65; \geq 65) and sex. Continuous data will be presented as mean with standard deviation or median with interquartile range and between group differences will be tested with the Student's t test and the Mann-Whitney U test, respectively. Categorical data will be presented as frequencies and percentages and will be compared using the chi-squared test or the Fisher exact test, as appropriate. All p values will be two-sided with values \leq 0.05 indicating statistical significance. Statistical tests will be done using the SPSS 24.0 statistical software (IBM Corp, Armonk, New York). Statistical analysis will be performed by statisticians affiliated with the Lady Davis Institute for Medical Research (Montreal, Quebec).

References

1. Kardia SL, Modell SM and Peyser PA. Family-centered approaches to understanding and preventing coronary heart disease. *American Journal of Preventive Medicine*. 2003;24:143-51.

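### Relatives with known non-coronary atherosclerotic disease and no recent CV screening can enter both primary-prevention measures, and may inflate the count above 10% risk

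*Combined protocol and SAP*

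**What the plan says.** Two criteria under Patient Identification and Recruitment turn on the CV status of the relatives and household members themselves. One removes "family or household members who have been screened for CV disease in the previous 2 years". The other is the only criterion based on a diagnosis: "Family or household members with known coronary disease will also be excluded". Relatives must be at least 18 and have no upper age limit; the limit of 70 applies to the index patient.

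Risk Factor Screening and Treatment describes the visit in these terms: "CV primary prevention assessment will follow the Canadian Cardiovascular Society's recommendations". A cardiologist takes a targeted history, and a modified 10-year Framingham score is calculated.

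Measures defines two outcomes. Screening effectiveness is the "total number of participants identified at intermediate or high risk on the modified Framingham CV risk score", with the threshold given as ">10% risk of a CV event over the following 10-year period". The second outcome is introduced as follows: "The effectiveness of the primary prevention intervention will be measured by the change in percentage of the mean modified Framingham 10-year CV risk score", taken from the initial visit to 6 months in family and household members.

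For relatives, Data Collection lists symptoms, medications, examination findings and risk factors, but has no item for prior CV disease. Data Analysis has no rule that removes such participants or reports them separately.

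**The concern.** The eligibility rule is narrower than the question. The plan speaks of primary prevention of CV disease, and its score refers to CV events in general. The evident reason for leaving out people with known coronary disease is that they are past primary prevention. That reason applies equally to someone with a prior stroke or peripheral arterial disease, yet the rule does not reach them.

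Two results are exposed. The first is a raw count, so every such person above the threshold adds one to it, although their established disease was known before the visit. The second is a mean change over 6 months, in which the course of people with established disease would be averaged with that of people without it, under a primary-prevention label. With no upper age limit, parents, older siblings and partners are eligible, so enrolment of such people is plausible.

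**Working it through.** **Plan's own figure.** There is none to reproduce. The documents give no sample size, expected yield, score distribution or prevalence of non-coronary CV disease.

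**Step 1: can such a person enter both measures?** Take a relative with a stroke some years ago and no CV screening in the previous 2 years.

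- Known coronary disease: no, so not excluded.
- Screened in the previous 2 years: no, so not excluded.
- Age: any age from 18 upwards qualifies.
- Scoring: the score is planned for those who attend, with no stated exception for prior CV disease.
- Analysis: neither Measures nor Data Analysis takes the person out.

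On the text as written, the person is scored and enters both measures.

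**Step 2: how much could this matter for the first measure?** All inputs are assumptions:

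- f = share of screened relatives with known non-coronary atherosclerotic CV disease, 1-5%
- p = proportion of them scoring above 10%, 70-100%
- y = proportion of the other relatives scoring above 10%, 20-40%

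Share of the count that comes from these people = f·p / (f·p + (1 − f)·y).

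Observed proportion above 10% = f·p + (1 − f)·y, so the shift from y is f·(p − y).

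| f | p | y | Share of count | Observed proportion | Shift |
|---|---|---|---|---|---|
| 0.01 | 0.7 | 0.4 | 0.007/0.403 = 1.7% | 40.3% | 0.3 points |
| 0.03 | 1.0 | 0.3 | 0.030/0.321 = 9.3% | 32.1% | 2.1 points |
| 0.05 | 1.0 | 0.2 | 0.050/0.240 = 20.8% | 24.0% | 4.0 points |

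The first and last rows are the two ends of the range. The largest value needs the highest f, the highest p and the lowest y together.

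**Step 3: does the direction depend on the assumptions?** The count can only rise or stay the same when these people are included. The proportion follows the sign of p − y. To test this, let f run from 1% to 10% and p from 20% to 100%, with y still 20-40%:

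- f = 10%, p = 100%, y = 20%: shift = 0.10 × 0.80 = +8.0 points; share of count = 0.10/0.28 = 35.7%.
- p = y = 20%: shift = 0 at any f.
- f = 10%, p = 20%, y = 40%: shift = 0.10 × (−0.20) = −2.0 points.
- f = 1%, p = 20%, y = 40%: share of count = 0.002/0.398 = 0.5%.

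The effect on the count thus runs from negligible to material, and the proportion can move either way.

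**Second measure.** The documents give no basis for the size or direction of the effect on the 6-month change, so no figure is offered.

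**The case against.** A reader might infer that coronary disease is the only thing that keeps a relative out, and that the yield is therefore inflated. The documents support neither statement in that form.

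- **The affected group is narrower.** The 2-year screening exclusion should remove some people with established disease who are under recent care. This stands, but it does not close the gap: the protocol does not define screening, and an older diagnosis without recent screening passes through.
- **Inflation is not shown.** Not one such person need enrol, and nothing in the documents says how often they would score above 10%. The range of 70-100% builds in the direction. This stands; only the statement that the count cannot fall is independent of the inputs.
- **A share of 2-21% sounds larger than it is.** The same inputs move the proportion by 0.3 to 4 points. The count also has no target, comparator or decision rule, so no conclusion is shown to change. This stands too, although the raw count is the measure that the plan chose.
- **It may be handled in practice.** The cardiologist's history could reveal prior disease, and the cited national recommendations may limit who is scored. The recommendations cannot be checked here. The protocol states no exception and attaches no data item or analysis rule to the history.
- **The measure classifies risk and does not count new diagnoses.** That is a fair reading of Measures: a person with a prior stroke can still be newly classified as above 10%. It does not explain why known coronary disease is excluded and comparable disease elsewhere is not.

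**Conclusion.** The point holds as a mismatch between the eligibility rule and the plan's own primary-prevention question. Relatives with known non-coronary atherosclerotic CV disease and no recent screening are eligible, and as written they contribute to both effectiveness measures. The count above 10% may be inflated as a result; that it will be inflated is not established.

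The table's range is an illustration on assumed inputs, not an estimate for this study, and the true effect may be small. For the 6-month change in mean score, what can be said is that the analysed group would not match its label. This is a minor point, worth making because the remedy is cheap.

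**What to change.** Add known non-coronary atherosclerotic CV disease (for example prior stroke or peripheral arterial disease) to the baseline items for relatives under Data Collection. Then choose one of two rules and state it before analysis:

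1. Extend the exclusion under Patient Identification and Recruitment from known coronary disease to any known atherosclerotic CV disease.
2. Let these relatives attend, but leave them out of both the count above 10% and the 6-month change in mean score, and report their number separately.

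Either rule should refer to disease known before the screening visit, so that anything first found by the programme is still credited to it. The second keeps the programme open to all who come and shows how many people are affected. The cost is one data item, one sentence in eligibility or in the definition of the analysis set, and slightly fewer analysed participants.

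### The 6-month risk-score change has no comparator and no stated analysis, and every named test treats relatives of the same patient as independent

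*Combined protocol and SAP*

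**What the plan says.** Measures gives two yardsticks. Screening is judged by the number of participants above 10% on the modified Framingham 10-year score. For the intervention, "The effectiveness of the primary prevention intervention will be measured by the change in percentage of the mean modified Framingham 10-year CV risk score", in family and household members, from the initial visit to 6 months.

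The data for a within-person analysis will exist. Data Collection records individual risk factors "as well as baseline and 6-month modified Framingham 10-year risk scores", and under Risk Factor Screening and Treatment, at 6 months "participants will receive an individualized report of CV risk factor control and their change in 10-year modified CV risk".

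Data Analysis stratifies results by age (below 65, and 65 or over) and by sex. For continuous data, "between group differences will be tested with the Student's t test and the Mann-Whitney U test, respectively". Categorical data "will be compared using the chi-squared test or the Fisher exact test, as appropriate". No other test or model is named.

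Several members can come from one patient. Patient Identification and Recruitment requires at least one relative or household member and sets no maximum. Data Collection asks each patient for the "approximate number of eligible family or household members". Risk Factor Screening and Treatment says that the patient and "all participating family and household members will be encouraged to attend the initial screening visit". The recruitment section also argues that household members share smoking, activity and dietary habits.

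**The concern.** There are three linked problems.

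- **Claim.** The word effectiveness attributes the change to the intervention. A single cohort measured twice cannot support that. The protocol itself points to another source of change: appointments are timed soon after the hospitalization "in order to maximize the motivation of family members who are willing to undergo screening". A relative's acute coronary event may alter behaviour whether or not a programme follows.
- **Missing method.** The change over 6 months is the only quantity that Measures designates for judging the intervention, yet Data Analysis does not say how its uncertainty will be estimated.
- **Independence.** Members who share an index patient are likely to resemble one another, for reasons the protocol gives. All four named tests assume independent observations. This affects any test of the change that ignores families. It also affects the age and sex comparisons, both of continuous results and of the proportion above 10% risk.

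At stake are an interval that may be too narrow, subgroup p values that may be wrong in either direction, and a causal conclusion that the design cannot support.

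**Working it through.** **What is given.** The two-sided 0.05 threshold is the only numerical input. The documents state no sample size, SD, family size, correlation or retention, so there is no planned figure to reproduce. The values of m (members per patient) and ρ (within-family correlation of the change) below are assumptions.

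**1. Match of measure to method.** The measure is a change within the same people. The two tests for continuous data are tied to differences between groups, and the only groups defined are age and sex strata. Comparing change scores between men and women would be a legitimate use of those tests, but it does not estimate the mean change itself. No paired, signed-rank, mixed-model or cluster-robust method appears.

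**2. Ignoring families in an otherwise correct paired analysis.** The design effect is DE = 1 + (Σm²/Σm − 1)ρ, which is 1 + (m − 1)ρ when families are of equal size. The actual type I error is 2[1 − Φ(1.96/√DE)], and the correct interval is √DE times as wide as the unclustered one.

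| Members per patient | ρ | DE | Type I error | Correct interval wider by |
|---|---|---|---|---|
| All bring 1 | any | 1.00 | 5.0% | 0% |
| 80% bring 1, 20% bring 2 | 0.1 | 1.033 | 5.4% | 2% |
| 80% bring 1, 20% bring 2 | 0.3 | 1.10 | 6.2% | 5% |
| All bring 2 | 0.1 | 1.10 | 6.2% | 5% |
| All bring 2 | 0.3 | 1.30 | 8.6% | 14% |
| All bring 3 | 0.1 | 1.20 | 7.4% | 10% |
| All bring 3 | 0.3 | 1.60 | 12.1% | 26% |

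For the 80/20 mix, per patient Σm = 0.8 × 1 + 0.2 × 2 = 1.2 and Σm² = 0.8 × 1 + 0.2 × 4 = 1.6. So Σm²/Σm − 1 = 0.333, and DE = 1.033 at ρ = 0.1 and 1.10 at ρ = 0.3.

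**3. Age and sex comparisons, all members in pairs, same values of ρ.**

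- Both relatives in the same group (two sisters, in a comparison by sex): unclustered over correct standard error = 1/√(1 + ρ) = 0.95 to 0.88, too small.
- Relatives in different groups (husband and wife): 1/√(1 − ρ) = 1.05 to 1.20, too large.

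Real families will mix the two, so the direction cannot be stated in advance.

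**4. Unit.** The phrase about a change in percentage has two readings. If mean risk went from 12% to 10% (illustrative), the change would be 10 − 12 = −2.0 points, or −2/12 = −16.7% of the baseline mean.

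**The case against.** The strongest reply is that this is an omission and not a wrong method. That is right for the 6-month change. A reader might infer that unpaired tests will be run on the two visits. With equal SDs and a correlation r of 0.5 to 0.9 between a person's two scores, that would make the standard error 1/√(1 − r) = 1.4 to 3.2 times too large. The documents do not support this reading: the tests are assigned to between-group differences, and no text applies them to the two visits or promises a p value for the change. Those ratios describe a misuse the plan does not state and form no part of the size of this point. For the age and sex comparisons, however, the tests are stated, and they do ignore families.

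Second, families may be small. That also stands. Data Collection records the number eligible, not enrolled, and if nearly every patient brings one member the clustering matters little. The 12.1% needs three members from every patient and ρ = 0.3.

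Third, effectiveness may be only a label, since no causal hypothesis is written and the strategy deliberately uses motivation after the event. This has some force, but the sentence names the intervention as the thing being measured, and without a comparator the effect of the event cannot be separated from that of the programme.

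Two further inferences go too far. The 6-month change is not the only information on the intervention: individual risk factors are recorded at both visits, and the Information Assessment Method questionnaire asks about practical impact and expected benefit. Nor is the screening result wholly untouched: the unstratified count is unaffected, but its comparison by age and sex is.

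**Conclusion.** The point holds as a gap in the specification, a flaw in the stated subgroup tests, and an overclaim in wording. The design supports an observed before-after change in estimated risk. The plan names no method for that change, and none of its named tests allows for relatives who share an index patient.

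The size of the clustering problem is uncertain. With assumed within-family correlation of 0.1 to 0.3, it runs from none (one member per patient) to a type I error of 12.1% and an interval that should be 26% wider (three members from every patient). The subgroup comparisons may err in either direction.

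This should be corrected before analysis. It does not make the data unusable. The unit of change and the handling of members without a 6-month score are lesser points of clarification.

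**What to change.** **Data Analysis.** Add: *For family and household members with both scores, the mean within-person change (6 months minus baseline) will be reported with a 95% CI from a paired analysis with standard errors clustered on the index patient. The age and sex comparisons, continuous and categorical, will use the same clustering.*

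**Data Collection.** Record an index-patient identifier for each member. The listed relationship to the patient gives the type of tie, not which patient, so it cannot define the family. The link is easy to capture because members are referred through that patient's letter.

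**Measures.** Report the result as *observed change in estimated CV risk after screening and management*, and state that without a comparator it does not estimate intervention effectiveness.

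**Clarifications.** State whether the change is in percentage points or relative to the baseline mean. Tabulate baseline risk for members with and without a 6-month score.

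**Cost.** One extra data field, a little more analysis, and no new visits or clinical measurements. The claim becomes more modest and the interval possibly wider. The main estimate describes only members with both scores; the table shows how they differ from the rest at baseline but does not remove bias from selective return. Clustered standard errors can be slightly too small with few families: in simulation with 20 families of one to four members and ρ of 0.1 to 0.3, the type I error was 5.5 to 5.8%.

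### Does the plan need prespecified results for younger relatives and non-genetic household members?

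*Combined protocol and SAP*

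**What the plan says.** Patient Identification and Recruitment explains why two groups are admitted. Household members are included because "partners and other non-genetically related household members, who do not have the same hereditary predisposition as the patient with CV disease" nonetheless share habits and social influences with the patient. Adults from age 18 are included because "Younger relatives (typically under age 30) have been excluded from most prior screening studies" and because "Early risk factor assessment and counselling of younger patients may promote lifelong changes in lifestyle choices and behaviours with long-term benefits".

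Risk Factor Screening and Treatment states that, for those aged 30 or under, "a 30-year Framingham risk score will also be obtained" at the initial visit. Data Collection lists "age, sex, gender, ethnicity, relationship with CV patient" among the items taken from family and household members, and adds: "A 30-year Framingham risk score will be recorded at baseline and 6-months for patients who are under age 30", with age fixed at enrolment.

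Measures defines two effectiveness measures. One is the number of participants above 10% on the modified Framingham 10-year score. The other is the "change in percentage of the mean modified Framingham 10-year CV risk score for family and household members" from the initial visit to 6 months.

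Data Analysis says "Results will be stratified by age" (below 65; 65 and over) and sex. It then gives general rules for describing continuous and categorical data and for two-sided tests at 0.05.

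**The concern.** The protocol argues for each group on its own terms and collects the data that would describe it, but the analysis section names neither group. The stratum below 65 merges people in their twenties with people in their early sixties, and relationship is not a stratum. For the younger group the time horizon also seems mismatched: inclusion is justified by long-term gain, yet both measures look 10 years ahead, and the 30-year score is collected twice without a stated use.

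If that reading is right, any later statement about younger relatives or non-genetic household members would rest on a grouping chosen after the data were seen. Data Analysis provides for tests of between-group differences without listing groups beyond age at 65 and sex, which leaves room for such a choice.

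**Working it through.** The documents state no figure on this point: no sample size, group size, effect size or standard deviation. The check is therefore mainly a reading of the sections against each other, with arithmetic only on age spans and on precision under assumed cell sizes.

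**What is and is not named**

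| Item | Collected? | In either effectiveness measure? | Named stratum? |
|---|---|---|---|
| Age, cut at 65 | Yes | – | Yes |
| Sex | Yes | – | Yes |
| Age, cut near 30 | Yes (age recorded) | – | No |
| Relationship to patient | Yes | – | No |
| 10-year score | Both visits | Yes, both | – |
| 30-year score | Both visits, youngest only | No | – |

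The factual core of the concern is correct: 0 of 2 strata is relationship, and 0 of 2 measures uses the 30-year score.

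**Age span.** The stratum below 65 covers 64 − 18 + 1 = 47 single years of age, of which 29 − 18 + 1 = 12 are below 30. This counts years of age, not participants, so it says nothing about how many people are merged.

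**What is already fixed for the younger group.** Data Collection restricts the 30-year score to one age group, defined at enrolment, and to two visits. Data Analysis says how continuous data are to be summarised. Applying that rule to this variable gives a result for the youngest participants alone, at set times, with no cut-point left to choose. What remains unspecified is narrower: the score is not labelled a measure, and the 10-year results are not split near 30.

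**Age limit.** The two sections differ (30 or under; under 30). Only someone aged exactly 30 is treated differently.

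**What separate results could show.** Cell sizes here are assumptions. Proportions use exact (Clopper-Pearson) 95% intervals; for zero events the upper limit is 1 − 0.025^(1/n). The half-width for a mean change, in SD units, is t(0.975, n − 1)/√n.

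| Assumed n | 30% above threshold | Upper limit if none above | Mean change, ± SD |
|---|---|---|---|
| 10 | 3/10: 6.7–65.2% | 30.8% | 0.72 |
| 20 | 6/20: 11.9–54.3% | 16.8% | 0.47 |
| 40 | 12/40: 16.6–46.5% | 8.8% | 0.32 |
| 60 | 18/60: 18.8–43.2% | 6.0% | 0.26 |

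These treat participants as independent; correlation within families would widen them.

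**Would the obvious extra tables answer the questions?** Not cleanly. A row for under-30s mixes young relatives with young unrelated household members, so younger relatives are still not isolated unless age is crossed with relationship, which shrinks the cells further. A table by relationship alone is open to confounding by age: partners and adult children of a patient aged 70 or under may differ greatly in age, so a difference in the proportion above 10% could reflect age and not heredity. And reporting 10-year results in under-30s uses the very horizon said not to fit that group.

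**The case for a change.** The strongest case for a change is that these are the protocol's own open questions. It calls the best strategy for younger relatives unclear, adds a score for the youngest participants alone, and records relationship. Naming the results now would cost a few sentences and require almost no new data. Kept descriptive, with confidence intervals and no added tests, the results would bring no multiplicity. The sentence on means and medians mentions neither the 30-year score nor either group.

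Part of this stands. Naming the 30-year score as a descriptive secondary measure would make the plan tidier, and a result described in advance carries more weight than one that is not. But a reason for admitting a group is not a promise to estimate its effect separately, and the protocol states no subgroup hypothesis. The fear of a freely chosen age cut is also weak, since every mention of a younger group points to about 30. For relationship the freedom is real, but a table produced later and labelled exploratory would serve the same purpose, with the same need to take age into account.

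**Conclusion.** No change is needed. Followed as written, the plan yields both pooled 10-year measures without bias from this source, and no stated rule or number leads to a wrong result. The omission is a reporting gap that analysts can fill sensibly: age, relationship and both scores are recorded, so descriptive or exploratory tables remain possible and no information is lost.

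The effect on the trial's conclusions cannot be computed from the documents, and nothing in them suggests one. If about 20 people fell in a group, an observed 30% above the threshold would carry an interval of roughly 12% to 54%; even at 60 it would be 19% to 43%. Separate results of that precision would settle little.

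The differing age limits for the 30-year score are a clerical slip to be reconciled between the two sections. It touches only participants aged exactly 30 and neither effectiveness measure.

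This conclusion rests on reading the recruitment rationale as grounds for eligibility. Had the protocol set a subgroup objective, or intended to draw confirmatory conclusions about either group, the omission would matter.
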